7.5.4 Overall Survival Rate at 24 Months

The OS[24] for each treatment group will be estimated using the Kaplan-Meier (KM) product-limit method and the corresponding two-sided 95% confidence intervals using log-log transformation will be computed. There will be no hypothesis testing for this endpoint.

7.5.5 Relationship between OS or PFS and TMB

This analysis will not be generated at the time of the primary lock, because - due to limited tissue availability and the need to use the samples for the MGMT promoter methylation bridging study - TMB analysis was put on hold.

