1.3.2 Secondary Objectives

- To compare investigator-assessed PFS of RT + nivolumab versus RT + TMZ
- To estimate the OS rate at 24 months (OS[24]) of RT + nivolumab versus RT + TMZ (final analysis only)
- To evaluate, in newly diagnosed, unmethylated MGMT GBM, any relationship between OS or PFS and TMB in the RT + nivolumab arm compared to the RT + TMZ control.

[REDACTED]

[REDACTED]

[REDACTED]

[REDACTED]

[REDACTED]

[REDACTED]

[REDACTED]

[REDACTED]

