8 STATISTICAL CONSIDERATIONS

8.1 Sample Size Determination

This is a Phase 3, randomized, open label, multicenter study of RT + nivolumab versus RT + TMZ in adult (≥ 18 years) subjects with newly diagnosed GBM subjects with unmethylated MGMT tumors.

Primary objective of the study is to compare the OS of RT+ nivolumab versus RT+TMZ in subjects with newly diagnosed GBM subjects with unmethylated MGMT tumors after surgery.

The sample size for this study is based on the following assumptions:

- 1) OS follows exponential distribution
- 2) Median OS in RT + TMZ arm is 13.0 months (Weller 2009³⁴)
- 3) Hazard ratio (HR) of arm RT + nivolumab vs RT + TMZ is 0.72, translated to median OS improvement of 5.0 months (13.0 months vs 18.0 months for arm RT + TMZ and arm RT + nivolumab, respectively)

At least 390 events (ie, death) provides 90% power to detect a hazard ration (HR) of 0.72 with an overall type 1 error of 0.05 (two-sided). This translates to an observed HR of 0.82 (median OS of 13.0 vs 15.8 months) or less resulting in a statistically significant improvement.

Approximately 550 subjects will be randomized to the two arms (RT +nivolumab vs RT + TMZ) in a 1:1 ratio stratified by complete or partial resection at baseline. Accrual will take approximately 10 months. The total duration of the study from start of randomization to final analysis of OS is expected to be approximately 33 months (10 months of accrual + 23 months of follow-up, Table 8.1-1).

Power calculations were done using East v 6.3.

Table 8.1-1: Key parameters of Sample Size Calculation of OS

Assumptions	Analysis	Goal/Timing (from first subject randomized)	Significant Nominal p-value	Probability for declaring superiority Under HA/H0
$\alpha = 0.05$ Power = 90% Control arm (RT+TMZ) median OS = 13.0 months; Treatment arm (RT + Nivolumab) Median OS = 18.0 months HR = 0.72	Final Superiority	390 OS events/ 33 months	Superiority Observed nominal p-value ≤ 0.05	90%/5%

The PFS, overall survival at 24 months (OS[24]), and OS and PFS in TMB-high patients are secondary endpoints. OS[24] is included as secondary endpoint to evaluate the improvement in long term survival. Only PFS will be tested using a hierarchical testing procedure. (Section 8.4.2).

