8.3.2 Secondary Endpoint(s)

The first secondary objective (comparing PFS between arm RT + nivolumab and RT + TMZ) will be measured by the endpoint of PFS. PFS is defined as the time from randomization to the date of the first documented tumor progression or death due to any cause. Subjects who die without a reported progression will be considered to have progressed on the date of death. Subjects who did not have disease progression or die will be censored at the date of last tumor assessment. Subjects who did not have any on study tumor assessment and did not die will be censored at the randomization date. Subjects who started any subsequent anti-cancer therapy without a prior reported progression will be censored at the last tumor assessment prior to initiation of the subsequent anti-cancer therapy. Subjects who had surgical resection post start of study treatment will be censored at the last tumor assessment date prior to initiation of surgical resection. PFS will be determined by investigator reported response based on RANO criteria ([Section 5.4.3](#)).

The secondary objective (estimate the overall survival rate at 24 months (OS[24]) of RT + nivolumab) will be Kaplan-Meier probability of survival at 24 months.

The secondary objective is OS and PFS assessed in the TMB-high population, as assessed in the TMB assay where the numerical cut-off for high versus low will be specified in the statistical analysis plan (SAP). Definition for OS and PFS for this endpoint will be the same as defined earlier.

[REDACTED]

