8.4.2.2 Analyses of Secondary Endpoints

The comparison of PFS will be based on a two-sided log-rank test stratified by corresponding stratification factor (complete surgical or partial resection at baseline). The details of the testing procedure will be specified in the SAP. OS[24] will be estimated when all censored subjects have had follow-up of at least 24 months. OS and PFS in the TMB-high population will be estimated using the Kaplan-Meier method. Additional details for the analysis of OS[24] endpoint will be included in SAP.

[REDACTED]

[REDACTED]

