3.2 Secondary

- To compare investigator-assessed PFS of RT + nivolumab versus RT + TMZ
- To estimate the OS rate at 24 months (OS[24]) of RT + nivolumab versus RT + TMZ
- To evaluate, in newly diagnosed, unmethylated MGMT GBM, any relationship between OS or PFS and tumor mutational burden (TMB) in the RT+nivolumab arm compared to the RT+TMZ control arm

[REDACTED]

[REDACTED]

[REDACTED]

[REDACTED]

[REDACTED]

[REDACTED]

[REDACTED]

[REDACTED]

[REDACTED]

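### The TMB secondary objective asks about effect modification, but the only stated method is TMB-high Kaplan-Meier curves, and no readable SAP section gives the cut-off or an analysis before the primary lock

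*SAP*

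**What the plan says.** - **Objective.** Protocol 1.3.2 asks about "any relationship between OS or PFS and TMB in the RT + nivolumab arm compared to the RT + TMZ control". SAP 3.2 keeps the same secondary objective.
- **Endpoint and cut-off.** Protocol 8.3.2 turns the objective into OS and PFS in a TMB-high population, with the "numerical cut-off for high versus low will be specified in the statistical analysis plan (SAP").
- **Method.** Protocol 8.4.2.2 says "OS and PFS in the TMB-high population will be estimated using the Kaplan-Meier method". The synopsis and Protocol 8.4.2 say the same.
- **Testing.** Protocol 8.1: "Only PFS will be tested using a hierarchical testing procedure".
- **SAP 3.0.** Section 6.3 defines a TMB-evaluable population, namely randomized subjects with a baseline TMB value. Section 7.5.5, the section for this analysis, is one sentence: "This analysis will not be generated at the time of the primary lock". The reason given is limited tissue and the competing need for samples in the MGMT bridging study, so "TMB analysis was put on hold".

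**The concern.** The objective compares a relationship between arms: does the treatment effect on OS or PFS change with TMB? That is a treatment-by-TMB interaction. Curves by arm in TMB-high subjects alone do not address it, because they contain nothing to compare that subgroup with.

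The cut-off that defines the subgroup was left to the SAP and is not in its readable text. SAP 7.5.5 then moves the analysis past the lock that delivers OS by arm, in an open-label trial (SAP 2.3), without saying how or when the cut-off will be set. If it were set after the OS result, the TMB-high estimate would be open to outcome-driven choice. What is at stake is the credibility of one secondary objective, not the primary conclusion.

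**Working it through.** **1. What the stated method can show.** Take two hypothetical situations, using the design HR of 0.72 for TMB-high in both:
- A: HR 0.72 in TMB-high and 0.72 in TMB-low. Ratio of HRs = 0.72/0.72 = 1.00, so no effect modification.
- B: HR 0.72 in TMB-high and 1.00 in TMB-low. Ratio = 0.72/1.00 = 0.72, so TMB is predictive.

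With the same control-arm survival, the expected TMB-high curves are identical in A and B. Only a TMB-low estimate or an interaction term tells them apart, and the readable text of both documents contains neither. It contains no model with continuous TMB either.

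**2. Where the cut-off should be.** Protocol 8.3.2 sends the reader to the SAP. The readable part of SAP 4.2 covers PFS and OS[24] only. SAP 6.3 defines TMB-evaluable but not TMB-high or TMB-low. SAP 7.5.5 gives no cut-off, method or restart trigger. Parts of the SAP are redacted or removed, so the statement is limited to readable sections; 7.5.5 itself is readable.

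**3. The plan's own figure.** The TMB endpoint has no sizing. The OS sizing reproduces: events = 4(1.960 + 1.282)²/(ln 0.72)² = 390, and the critical HR = exp(−2 × 1.96/√390) = 0.820, matching Protocol 8.1. It serves below only as the number of deaths to be split.

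**4. Illustration of a free choice of cut-off.** Assumptions: no treatment effect at any TMB level; exponential OS with a 13-month median; follow-up of 23 to 33 months; 150, 300 or 450 evaluable subjects (the documents give no number); log-rank test in subjects at or above each of 13 percentiles, 20th to 80th in steps of 5; 2,000 trials per size.
- Any cut-off with |Z| > 1.96: one set of runs gave 20.0%, 19.2% and 17.6% for the three sizes; a second gave 18.0%, 17.8% and 18.8%; further runs gave about 17% to 18%. The standard error of one estimate near 18% is √(0.18 × 0.82/2,000) = 0.9 percentage points, so these agree reasonably well.
- In favour of nivolumab only: about 8% to 10%, against 2.5%.
- One fixed cut-off at the median: 5.2% to 5.8%.

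**5. How precise an interaction would be.** Assume all subjects are evaluable and split 390 deaths in proportion to TMB-high prevalence, which is also assumed. SE of the log HR in TMB-high = 2/√d_high. SE of the log ratio of HRs = √(4/d_high + 4/d_low). Ratio detectable with 80% power = exp(−2.80 × SE).

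| TMB-high share | Deaths high / low | 95% CI around HR 0.72 in TMB-high | Detectable ratio of HRs |
|---|---|---|---|
| 10% | 39 / 351 | 0.38 to 1.35 | 0.39 |
| 25% | 98 / 293 | 0.48 to 1.07 | 0.52 |
| 50% | 195 / 195 | 0.54 to 0.95 | 0.57 |

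If only half are evaluable, the detectable ratios are 0.26, 0.40 and 0.45.

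**The case against.** The strongest reply has five parts.

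- **No test is planned.** The endpoint is estimated only, so there is no 5% error rate to inflate. This stands. A reader might infer from the simulation that trial type I error is at risk; Protocol 8.1 and 8.4.2 do not support that. The percentages only illustrate how far a free cut-off can mislead a nominal comparison.
- **The SAP does not say the cut-off will be chosen after OS is known.** This also stands. A reader might infer such a plan, but SAP 7.5.5 says only that the work is on hold and will miss the primary lock. A later SAP version could still fix the cut-off before TMB is linked to outcome. The weakness is that nothing written requires it.
- **The SAP is not committed to TMB-high curves.** Correct: SAP 7.5.5 states no method, and the Kaplan-Meier method is the Protocol's. A reader might conclude that the objective can never be answered; that goes too far. TMB-high curves by arm do describe the treatment difference in that subgroup. They just do not show whether it differs elsewhere.
- **The hold has a stated reason.** Scarce tissue justifies delaying the assay, and the SAP discloses this. It does not explain the missing rule, because writing one uses no tissue.
- **An interaction estimate would be weak.** True, as step 5 shows. That argues for reporting it with its interval, not for reporting one subgroup alone.

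**Conclusion.** The point holds, at low severity. The objective concerns variation of the treatment effect with TMB, and the only stated method cannot show it. The cut-off assigned to the SAP is in no readable section of version 3.0, and the deferral in SAP 7.5.5 carries no method, trigger or safeguard. A cut-off chosen with knowledge of OS by arm is therefore a risk, not a stated plan.

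The primary OS test, the PFS hierarchy and the type I error rate are untouched. The illustrative size, about 17% to 20% in either direction or 8% to 10% in favour of nivolumab, rests on assumed evaluable numbers, an assumed search over 13 cut-offs and a nominal test that the plan does not contain. The conclusion on method rests on none of these.

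**What to change.** Amend SAP 7.5.5 before the primary lock:

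1. In TMB-evaluable subjects, analyse OS and PFS with a Cox model stratified by resection, containing arm, continuous log TMB and their interaction. Report the interaction HR (with the log TMB unit stated) and its 95% CI, without a formal test.
2. Show Kaplan-Meier curves and HRs by arm in both TMB-high and TMB-low.
3. Fix the cut-off without outcome data. Use either a pre-stated external value, or a rule written now, such as a named percentile of the pooled TMB distribution, applied once the assay has run and before TMB is linked to outcome. The rule can be written during the hold; the trial's own TMB distribution cannot be assumed available before the lock.
4. Compare baseline features of TMB-evaluable and non-evaluable subjects, because limited tissue may make the evaluable group selective.
5. If the assay will not resume, formally withdraw the endpoint.

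The cost is SAP wording, one model and one baseline table, with no samples beyond those the assay already needs. The downside is an imprecise interaction estimate, which the interval will show.

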7.5.6 Other Efficacy Analyses

7.5.6.1 Analysis of Objective Response Rate

The number and percentage of subjects in each category of BOR per investigator (complete response [CR], partial response [PR], stable disease [SD], progressive disease [PD], or unable to determine [UTD]) will be presented, by treatment group. Estimates of response rate, along with its exact two-sided 95% CI by Clopper and Pearson⁹ will be presented, by treatment group. This analysis will be carried out on response-evaluable subjects.

A by-subject listing of best overall response will be presented including treatment group, best overall response per investigator and dates of CR/PR/progression.

A by-subject listing of per time point tumor assessments per investigator will be presented.

7.5.6.2 Time to Tumor Response and Duration of Response

Duration of response (DOR) and time to response (TTR) will also be evaluated for subjects who achieved confirmed PR or CR. The DOR for each treatment group will be estimated using the Kaplan-Meier (KM) product limit method and will be displayed graphically. A table will be produced presenting number of events, number of subjects involved, medians, and 95% CIs for the medians. The two-sided 95% CI in each treatment group will be computed based on a log-log transformation method.

TTR, which does not involve censoring, will be summarized by treatment group in all responders using descriptive statistics.

A by-subject listing will be presented including treatment group, time to response, duration of response, whether the subject was censored for duration of response, and, if so, the reason.

7.5.6.3 Analyses of Tumor Burden

The magnitude of reduction in tumor burden in response evaluable subjects with on-study tumor assessment will be summarized descriptively.

[figure not shown]
The following subject-level graphics will also be provided by treatment group as randomized:

- For all responders, time courses of the following events of interest will be graphically displayed: tumor response, progression, last dose received, and death.
- For response evaluable subjects with on-study tumor assessment, a waterfall plot showing the best reduction in measurable lesion based will be produced.
- For response-evaluable subjects with on-study tumor assessment, a plot of individual subjects' percent change in measurable lesion tumor burden from baseline will be produced.

7.5.6.4 Analysis of Subjects Treated beyond Progression

The following analysis may be conducted for subjects treated with RT plus nivolumab who are progressed:

- Summary of demographic and baseline characteristics by two groups (treated beyond initial progression or not treated beyond initial progression)
- Evaluation of survival for patients treated beyond initial progression vs. not treated beyond initial progression by a landmark analysis
- Plot of individual subjects' percent change in measurable lesion tumor burden from baseline.
- Time courses of the following events of interest will be graphically displayed in relation to OS: tumor response, progression, last dose received, on-treatment/subsequent surgery
- Summary of overall duration of treatment, number of doses received beyond initial progression, duration of treatment beyond initial progression.
- By-subject listing will include: overall duration of treatment, number of doses received beyond initial progression, duration of treatment beyond initial progression, OS

[REDACTED]

[REDACTED]

[REDACTED]

7.6.14 *Pregnancy*

A by-subject listing of pregnancy tests results will be provided for randomized female subjects.

[REDACTED]

[REDACTED]

[REDACTED]

[REDACTED]

[REDACTED]

[REDACTED]

[REDACTED]

[REDACTED]

[REDACTED]

[REDACTED]

[REDACTED]

[REDACTED]

[REDACTED]

[REDACTED]

[REDACTED]

[REDACTED]

[REDACTED]

[REDACTED]

[REDACTED]

[REDACTED]

[REDACTED]

[REDACTED]

[REDACTED]

9 CONTENT OF REPORTS

All analyses described in this SAP will be included in the Clinical Study Report(s) except where otherwise noted. Additional exploratory analyses may be performed. Refer to the Data Presentation Plan for mock-ups of all tables and listings.

10 DOCUMENT HISTORY

Table 10-1: Document History

Version Number	Author	Description
3.0	[REDACTED]	
Revision Date: 15-Jan-2019
 
Section 2 Study Description: Multiple changes are made in section 2 Study description in accordance with the amendments of the protocol.
 
Section 2.1 Study Design: “The treatment phase will consist of an induction phase (chemoradiation therapy) followed by 4 weeks break and maintenance temozolomide therapy” is added to define induction and maintenance phase for exposure analysis.

Table 10-1: Document History

Version Number	Author	Description
		
[REDACTED]
 
Sections 4.2.2 Overall Survival at 24 months, 7.5.1.1 Primary Analysis: A text is added that survival rate estimates can also be produced for timepoints beyond the minimum follow-up if it is judged appropriate.
 
Section 4.3 Exploratory Endpoint(s) is restructured: Subsection for [REDACTED]
 
[REDACTED]
 
[REDACTED]
 
[REDACTED]
 
[REDACTED]
 
[REDACTED]
 
[REDACTED]
 
[REDACTED]
 
Section 5 SAMPLE SIZE AND POWER: “The progression free survival (PFS) , overall survival at 24 months (OS[24]), and OS and PFS in TMB-high patients are secondary endpoints. OS[24] is included as secondary endpoint to evaluate the improvement in long term survival.” is deleted as irrelevant in this section.
 
[REDACTED]
 
[REDACTED]

Table 10-1: Document History

Version Number	Author	Description
		
Section 7.2.2 Relevant Protocol Deviations: new deviation “Subjects without baseline MRI scan”.
 
[REDACTED]
 
Section 7.3.1 Subject Disposition: Analysis population is specified; description of listings is updated to be compliant with the CRF and support the tables.
 
[REDACTED]
 
Section 7.3.4 Prior Therapy: Summaries of agents by name and by ATC class are specified.
 
Section 7.4.1 Administration of Study Therapy: The denominator for duration of treatment in months is corrected to 30.4375; definition of the last cycle length is corrected; terms “Dose Intensity”, “Relative Dose intensity” and the definitions are made compliant; populations for exposure analysis are restricted to subjects treated with a particular drug; definition of TMZ Dose (mg/m2) is corrected to be defined via BSA instead of weight; the following analyses for TMZ maintenance phase is removed: Cycles of treatment, Number of subjects completing 6 cycles; structure of the section is improved.
 
Section 7.4.2 Modifications of Study Therapy: Populations for exposure analysis is restricted to subjects treated with a particular drug.
 
Section 7.4.2.1 Nivolumab Dose delays: Definition of a delayed dose is added.
 
Section 7.4.2.3 Radiotherapy and Temozolomide is split to 7.4.2.3 Temozolomide Dose Modifications and 7.4.2.4 Missing Radiotherapy for compliance of the analyses with the CRF
 
[REDACTED]
 
Section 7.4.3.3 Subsequent Cancer Therapy is moved from 7.5. Efficacy; subsequent surgeries for “Other” reason and with a specification which includes ‘RESECTION’ will be accounted for subsequent therapy.
 
Section 7.5. Efficacy: Use of the stratification factor is specified.

Table 10-1: Document History

Version Number	Author	Description
		
Section 7.5.1.1 Primary Analysis: a by-subject listing is added.
 
Section 7.5.1.2 OS sensitivity Analyses: The covariate of prior surgery is delete from the multivariate analysis since the model is stratified by IVRS resection which would correlate with the covariate.
 
Section 7.5.3.1 Primary Analysis: Censoring categories are added; a by-subject listing is added.
 
Section 7.5.3.2 Sensitivity Analysis: Table 7.5.3.2-1 is replaced by figure 7.5.3.2-1.
 
Section 7.5.5 Relationship between OS or PFS and TMB: new analysis.
 
[REDACTED]
 
[REDACTED]
 
[REDACTED]
 
[REDACTED]
 
Section 7.6 Safety: Reference to Core Safety SAP is replaced by the appropriate text due to retirement of Core Safety SAP.
 
[REDACTED]
 
[REDACTED]
 
[REDACTED]
 
[REDACTED]
 
[REDACTED]
 
[REDACTED]
 
[REDACTED]
 
[REDACTED]
 
[REDACTED]

Table 10-1: Document History

Version Number	Author	Description
		
[REDACTED]
 
[REDACTED]
 
[REDACTED]
 
[REDACTED]
 
[REDACTED]
 
Throughout the document:
 
Multiple changes in the structure and language were made for the sake of compliance with the IO core SAP and without modification of the text meaning;
 
Multiple editorial changes.

2.0	[REDACTED]	
Revision Date: 19-Sep-2018
 
Revised SAP according to protocol amendment 09. Major changes included in this amendment are:
 
Removal of the interim analysis for superiority of the primary endpoint of OS.
 
Addition of a secondary endpoint that evaluated, in newly diagnosed, unmethylated MGMT GBM, any relationship between OS or PFS and TMB in the RT + nivolumab arm compared to the RT + TMZ control arm.

1.0	[REDACTED]	
Initial version dated 05-Jan-2017

APPENDIX 2 MISSING AND PARTIAL RADIOTHERAPY AND SURGERY DATES IMPUTATION ALGORITHMS

Procedures – Imputation Rules.

If reported procedure start date is a full valid date then set start date equal to the date part of procedure start date.

In case of partial date use imputation rules described below:

- If only day is missing then
 - If month and year of procedure match month and year of first dose date then impute as date of first dose;
 - If month and year of procedure don't match month and year of first dose date then impute as first day of that month and year.
- If both day and month are missing, then impute as maximum between 01JAN of the year and date of the first dose;
- If date is completely missing or invalid then leave missing.

Note: Imputation is not applicable to data where start date is not collected (for example "PRIOR RADIOTHERAPY" CRF). Set start date to missing in this case.

If reported end date is a full valid date then set end date equal to the date part of the reported end date.

In case of partial date use imputation rules described below:

- If reported end date is partial then set end date equal to the last possible reported end date based on the partial entered reported end date.
- If reported end date is missing, continuing, unknown or invalid then set end date equal to the most recent database extraction date.

If end date was imputed then compare end date to the death date or last known alive date if subject is not dead. If posterior then end date should be imputed to death date (or last known alive date if subject not dead).

Note: Imputation of partial dates only applies to data entered on "RADIOTHERAPY" CRF page. For other CRF pages in case of partial dates set end date to missing.

Surgeries – Imputation Rules.

If reported surgery date is a full valid date then set start date equal to the date part of surgery date.

In case of partial date, use one of the two imputation rules described below:

- 1) For data collected on "PRIOR SURGERY RELATED TO CANCER" CRF page:
 - a) If only day is missing then impute as the first day of the month;
 - b) If both day and month are missing then then impute as 01JAN of the year;

- c) If date is completely missing or invalid then leave missing.
- 2) B. For data collected on other CRF pages (deemed to be on-treatment/subsequent surgeries):
- a) If only day is missing then
 - i) If month and year of surgery match month and year of first dose date then impute the missing date as the date of first dose;
 - ii) If month and year of surgery don't match month and year of first dose date then impute as first day of that month and year;
 - b) If both day and month are missing then impute as maximum between 01JAN of the year and date of the first dose;
 - c) If date is completely missing or invalid then leave missing.
